## 11. REGULATORY CONSIDERATIONS

### 11.1. Institutional Review of Protocol

The protocol, the proposed informed consent and all forms of participant information related to the study (e.g. advertisements used to recruit participants) will be reviewed and approved by the

Stanford IRB and Stanford Cancer Institute Scientific Review Committee (SRC). Any changes made to the protocol will be submitted as a modification and will be approved by the IRB prior to implementation. The Protocol Director will disseminate the protocol amendment information to all participating investigators.

#### 11.2. **Data and Safety Monitoring Plan**

The Stanford Cancer Institute Data and Safety Monitoring Committee (DSMC) will be the monitoring entity for this study. The DSMC will audit study-related activities to determine whether the study has been conducted in accordance with the protocol, local standard operating procedures, FDA regulations, and Good Clinical Practice (GCP). This may include review of the following types of documents participating in the study: regulatory binders, case report forms, eligibility checklists, and source documents. In addition, the DSMC will regularly review serious adverse events and protocol deviations associated with the research to ensure the protection of human subjects. Results of the DSMC audit will be communicated to the IRB and the appropriate regulatory authorities at the time of continuing review, or in an expedited fashion, as needed.

#### 11.3. **Data Management Plan**

The Protocol Director, or his/her designee, will prepare and maintain adequate and accurate participant case histories with observations and data pertinent to the study. Study specific CRFs will document treatment outcomes for data analysis. CRFs will be developed using the OnCore database system and will be maintained by the study team. CRFs will be electronic and only accessible to the research team via password, dual-authentication database. All research charts will be kept in a locked office.

#### 11.4. **Study Monitoring**

The study will be monitored by Stanford's internal Data Safety Monitoring Committee (DSMC) on an annual basis per institutional guidelines.

#### 11.5. **Good Clinical Practice**

This study will be conducted in accordance with Good Clinical Practice (GCP), as defined by the International Conference on Harmonisation (ICH) and in accordance with the ethical principles

underlying European Union Directive 2001/20/EC and the United States Code of Federal Regulations, Title 21, Part 50 (21CFR50).

The study will be conducted in compliance with the protocol. The protocol and any amendments and the subject informed consent will receive IRB/IEC approval/favorable opinion prior to initiation of the study.

All potential serious breaches must be reported to Genentech immediately. A serious breach is a breach of the conditions and principles of GCP in connection with the study or the protocol, which is likely to affect, to a significant degree, the safety or physical or mental integrity of the subjects of the study or the scientific value of the study.

Study personnel involved in conducting this study will be qualified by education, training, and experience to perform their respective task(s). This study will not use the services of study personnel where sanctions have been invoked or where there has been scientific misconduct or fraud (e.g., loss of medical licensure, debarment).

Systems with procedures that ensure the quality of every aspect of the study will be implemented.

#### **11.6. Protocol Adherence**

The principal investigator must obtain IRB or IEC approval for the investigation. Initial IRB or IEC approval and all materials approved by the IRB or IEC for this study including the subject ICF and recruitment materials must be maintained by the investigator and made available for inspection.

Each investigator must adhere to the Protocol as described in this document and agree that changes to the Protocol, with the exception of medical emergencies, must be discussed and approved, firstly, by the sponsor or its designee and, secondly, by the IRB or IEC. Each investigator is responsible for enrolling subjects who have met the Protocol inclusion and exclusion criteria. The IRB that granted original approval, or the IRB currently responsible for overseeing the conduct of the study, must be notified of all changes in and deviations from the Protocol that may increase risk to the subject, and/or that may adversely affect the rights of the

subject or validity of the investigation. The investigator must send a copy of the approval letter from the IRB to the sponsor or its designee and retain the original in the site study regulatory file.

Major eligibility deviations must be reported to the IRB in accordance with the IRB requirements. During the course of the study, the monitor must notify the sponsor or its designee of subjects found not to have met eligibility criteria. The medical monitor, in collaboration with the investigator, will determine if the subject should be withdrawn from the study.

#### **11.7. Financial Disclosure**

All clinical investigators participating in clinical studies subject to FDA Regulation Title 21 Code of Federal Regulations (CFR) Part 54 – Financial Disclosure by Clinical Investigators, are required before study initiation to submit a completed Clinical Investigator Financial Disclosure Request Form that sufficiently details any financial interests and arrangements that apply. For the purpose of this regulation, clinical investigator is defined as any investigator or sub-investigator who is directly involved in the treatment or evaluation of research subjects, including the spouse and each dependent child of the clinical investigator. These requirements apply to both US and foreign clinical investigators conducting covered clinical studies.

Any new investigators or sub-investigators added to the covered clinical study during its conduct must also submit a completed Clinical Investigator Financial Disclosure Request Form. During a covered clinical study, any changes to the financial information previously reported by a clinical investigator must be reported to the sponsor or its designee. At the conclusion of the covered clinical study, the clinical investigators will be reminded of their obligation to report to the sponsor or its designee any changes to the financial information previously reported. The clinical investigators will also be reminded that they must report any changes in their financial information for a period of 1 year after completion of the covered clinical study.

#### **11.8. Compliance with Study Registration and Results Posting Requirements**

Under the terms of the Food and Drug Administration Modernization Act (FDAMA) and the Food and Drug Administration Amendments Act (FDAAA), the Sponsor of the study is solely responsible for determining whether the study and its results are subject to the requirements for submission to the Clinical Trials Data Bank, <http://www.clinicaltrials.gov>. Information posted

will allow subjects to identify potentially appropriate studies for their disease conditions and pursue participation by calling a central contact number for further information on appropriate study locations and study site contact information.

## 11.9. **Quality Control And Quality Assurance**

### 11.9.1. **Pharmaceutical Company Audits**

At some point during the study, individuals from the Merck and/or Incyte Quality Assurance department and/or their authorized representative may visit the investigator's site to conduct an audit of the study. The purpose of this visit will be to determine the investigator's adherence to the protocol, applicable regulations, and outlined procedures, in addition to assessing the accuracy of the study data. Before initiating this audit, the investigator will be contacted by the company(ies) to arrange a convenient time for this visit. The investigator and staff are expected to cooperate with the auditors and allow access to all subject records supporting the CRFs and other study-related documents.

### 11.9.2. **Inspection by Regulatory Authorities**

At some point during the investigational product's development program, a regulatory authority may visit the investigator to conduct an inspection of the study and the site. The investigator and staff are expected to cooperate with the inspectors and allow access to all source documents supporting the CRFs and other study-related documents. The investigator must immediately notify the sponsor when contacted by any regulatory authority for purposes of conducting an inspection.

## 11.10. **Ethics**

### 11.10.1. **Ethical Conduct of the Study**

This study will be performed in accordance with ethical principles that have their origin in the Declaration of Helsinki and conducted in adherence to the study Protocol, GCPs as defined in Title 21 of the US CFR Parts 50, 54 56, 312, and Part 11, as well as ICH GCP consolidated guidelines (E6) and applicable regulatory requirements.

### 11.10.2. **Ethics Review**

It is the responsibility of the investigator to assure that all aspects of the ethics review are conducted in accordance with the Declaration of Helsinki as described in the ICH E6: Guideline for GCP, and/or local laws, whichever provides the greatest level of protection for the study participants. The Protocol and any information supplied to the subject to obtain informed consent, including written ICFs, subject recruitment procedures (e.g., advertisements), and written information to be provided to subjects (information leaflets), must be reviewed and approved by a qualified IRB/IEC before enrollment of participants in the study. Before initiation of the study, the sponsor or its designee must receive documentation of the IRB or IEC approval, which specifically identifies the study/Protocol, and a list of the committee members.

The principal investigator is responsible for informing the IRB or IEC of any amendment to the Protocol in accordance with local requirements. Protocol amendments and revisions to the ICF must be submitted to and approved by the IRB or IEC.

Investigators must submit progress reports to the IRB or IEC in accordance with the IRB or IEC requirements and local regulations. Annual re-approval of the study must be obtained. Copies of progress reports and annual re-approvals must be sent to the sponsor or its designee.

The principal investigator is also responsible for providing the IRB or IEC with reports of any reportable serious adverse drug reactions from any other study conducted with the investigational product. The sponsor or its designee will provide this information to the principal investigator.

When the sponsor or its designee provides the investigator with a safety report, the investigator is responsible for ensuring that the safety report is reviewed and processed in accordance with regulatory requirements and with the policies and procedures established by their respective IRBs.

After completion or termination of the study, the investigator must submit a final report to the IRB or IEC and to the sponsor or its designee.

The investigator, as part of the records retention requirements for the study, must maintain documentation of all submissions, correspondence, and approvals to and from the IRB or IEC.

Each clinical investigator is responsible to conduct the study in accordance with the Protocol, all applicable laws, regulations, and GCP according to ICH guidelines.

#### 11.11. **Data Privacy**

The investigator and the sponsor or its designee must adhere to applicable data privacy laws and regulations. The investigator and the sponsor (or its designee) are responsible for ensuring that sensitive information is handled in accordance with local requirements (eg, HIPAA). Appropriate consent and authorizations for use and disclosure and/or transfer (if applicable) of protected information must be obtained.

#### 11.12. **Data Handling and Record Keeping**

##### 11.12.1. **Inspection of Records**

The investigator must ensure that all records pertaining to the conduct of the clinical study (as listed above) are adequately maintained for a period of 2 years after the last approval of a marketing application in an ICH region and until there are no pending or contemplated marketing applications in an ICH region, or at least 2 years have elapsed since the formal termination of clinical development of the investigational product.

##### 11.12.2. **Retention of Records**

The principal investigator must maintain all documentation relating to the study for a period of 2 years after the last marketing application approval, or if not approved, 2 years following the termination of the test article for investigation. If it becomes necessary for the sponsor or the regulatory authority to review any documentation relating to the study, the investigator must permit access to such records.

The investigator must not destroy any records associated with the study without receiving approval from Incyte and/or Merck. The investigator must notify the sponsor or its designee in the event of accidental loss or destruction of any study records. If the investigator leaves the institution where the study was conducted, the sponsor or its designee must be contacted to arrange alternative record storage options.

Whenever possible, an original recording of an observation must be retained as the source document. However, a photocopy of a record is acceptable, provided it is legible and is a verified copy of the original document.

All CRF data entered by the site (including audit trail), as well as computer hardware and software (for accessing the data), will be maintained or made available at the site in compliance with applicable record retention regulations.

### 11.13. Confidentiality

Subject names will not be supplied to Merck, Incyte or its designee if applicable. Only the subject number and subject's initials will be recorded in the CRF, where permitted; if the subject's name appears on any other document (e.g., laboratory report), it must be obliterated on the copy of the document to be supplied to the sponsor or its designee. Study findings stored on a computer will be stored in accordance with local data protection laws. The subjects will be informed that representatives of the sponsor or its designee, IRB or IEC, or regulatory authorities may inspect their medical records to verify the information collected, and that all personal information made available for inspection will be handled in strictest confidence and in accordance with local data protection laws.

## 12. STATISTICS CONSIDERATIONS

### 12.1. Statistical Design

This is a single-stage study for the doublet epacadostat and pembrolizumab. A 6-month PFS of 20% was observed using single agent pembrolizumab and is the basis for the null hypothesis of the present study (Bang, abstract 4001, GI ASCO 2015). We will enroll 30 patients over 18 months and follow patients for at least 6 months. This design has 80% power to reject a 20% PFS rate, if the true PFS is 39%. Calculation based on binomial probabilities with a one-sided significance of 10%. The level of significance for the primary endpoint in Phase 2 is one-sided 10%, which is deemed acceptable for a proof-of-concept study.

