## PROTOCOL SYNOPSIS

TITLE	Phase II Study Of Epcadostat (INCB024360) With Pembrolizumab (MK-3475) In Metastatic Or Unresectable Gastroesophageal Junction And Gastric Adenocarcinoma Requiring Paired Biopsies
STUDY PHASE	II
INDICATION	Metastatic or unresectable gastroesophageal junction or gastric adenocarcinoma having progressed on at least one line of prior therapy for metastatic disease
INVESTIGATIONAL PRODUCTS	Epcadostat (INCB024360) Pembrolizumab (MK 3475)
PRIMARY OBJECTIVE(S)	To assess 6-month progression free survival (PFS)
SECONDARY OBJECTIVE(S)	To evaluate response rate (RR), overall survival (OS), and the safety and tolerability of Epcadostat (INCB024360) in combination with Pembrolizumab (MK3475) by CTCAE v5
TREATMENT SUMMARY	Non-randomized, single arm, open-label Oral Epcadostat at 300 mg twice daily + Intravenous Pembrolizumab at 200 mg every 3 weeks for up to 24 months
SAMPLE SIZE	30 patients undergoing pre- and on-treatment tumor biopsies
STATISTICAL CONSIDERATIONS	This is a single-stage study for the doublet epcadostat and pembrolizumab. A 6-month PFS of 20% was observed using single agent pembrolizumab and is the basis for the null hypothesis of the present study [1]. We will enroll 30 patients over 18 months and follow patients for at least 6 months. This design has 80% power to reject a 20% PFS rate, if the true PFS is 39%. Calculation based on binomial probabilities with a one-sided significance of 10%.

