## **2. BACKGROUND**

### **2.1. Study Disease**

Gastroesophageal junction (GEJ) and gastric adenocarcinomas constitute a major health problem worldwide. Gastric cancer is the fourth most prevalent malignancy and the second leading cause of cancer death worldwide [2]. In the United States, an estimated 24,590 cases of gastric cancer will be diagnosed and 10,720 patients will die from this disease in 2015 [3]. Esophageal cancer is overall less common, but the incidence of adenocarcinoma of the esophagus, GEJ and gastric cardia has risen faster than any other malignancy in the last 25 years in the United States and other Western countries [4]. Although treatment for patients with unresectable or metastatic disease remains palliative, chemotherapy improves survival and quality of life when compared to best supportive care [5]. With standard treatment options, the progression free survival (PFS) for unresectable or metastatic disease is 4 to 6 months and median overall survival (OS) is 7 to 10

months. Recent trials in the second-line setting have shown median PFS is 2-3 months and median OS is 3-5 months [6, 7].

Data are emerging to suggest a role for checkpoint modulators in GEJ/gastric cancers and include antibodies against PD-L1 (atezolizumab)[8] and CTLA-4 (tremelimumab) [9]. Most recently, the KEYNOTE-012 study (NCT01848834), a multicenter, open-label, study of intravenous pembrolizumab included a cohort of 39 patients with PD-L1 expressing advanced gastric cancer. The majority of patients received  $\geq 2$  prior therapies. The 6-month PFS was 26%; median PFS was 1.9 months. 6-month OS was 66%, median OS was 11.4 months. 22% of patients achieved a partial response (PR) and 14% achieved stable disease as measured by RECIST v1.1 and central review.[1]

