highest cut point (proportions score  $\geq 50\%$ ) referred to as PD-L1 strong tumors, and tumors expressing  $> 1\%$  but  $< 50\%$  referred to as the PD-L1 weak tumors. Outcomes based in irRC were used as the primary outcome for the analysis. Based on the training set, the positive predictive value for subjects in the strong category was 42%, while maintaining a negative predictive value of 92% for subjects in the weak or null category.[55] This study completed, and a total of 495 subjects received pembrolizumab either 2 mg/kg every 2 weeks or 10 mg/kg every 3 weeks or 10 mg/kg every 2 weeks, and 182 subjects were assigned to the training group or a validation group (313 subjects). Among all subjects, the ORR was 19.4%, and the median duration of response was 12.5 months. The median duration of PFS was 3.7 months, and the median duration of OS was 12.0 months. PD-L1 expression in at least 50% of tumor cells was selected as the cutoff from the training group. Among subjects with a proportion score of at least 50% in the validation group, the response rate was 45.2%. Among all subjects with a proportion score of at least 50%, median PFS was 6.3 months; median OS was not reached. In summary, pembrolizumab had an acceptable side-effect profile and showed antitumor activity in subjects with advanced NSCLC. PD-L1 expression in at least 50% of tumor cells correlated with improved efficacy of pembrolizumab.[56]

Data are emerging to suggest a role for checkpoint modulators in GEJ/gastric cancers and include antibodies against PD-L1 (atezolizumab)[8] and CTLA-4 (tremelimumab).[9] In an open-label, Phase 1b study, the safety, tolerability, and antitumor activity of pembrolizumab were assessed in subjects with advanced solid tumors in the KEYNOTE-012 study (Clinicaltrials.gov: NCT01848834). In this study a cohort of 39 patients with PD-L1 expressing advanced gastric cancer, 22% of patients achieved a partial response (PR) and 14% achieved stable disease as measured by RECIST v1.1 and central review.[57]

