#### 4.9.3. **Tumor Biopsy**

Fresh tumor biopsies (defined as a biopsy specimen taken since completion of the most recent prior chemotherapy regimen) will be required at baseline and on treatment of the same lesion (day 42  $\pm$  5 days). Patients are not required to have PD-1 expression testing for enrollment on the study. All sites of disease that are amenable to biopsy are allowable per protocol. Measurable lesions that are the only site of measurability per RECIST v1.1 cannot be biopsied due to obstruction of measurement. Additionally, previously irradiated lesions cannot be biopsied due to potential for necrotic and nonviable tissue.

Standard techniques will be used for all biopsies, which may include CT, ultrasound, or endoscope depending on site of biopsiable lesion. The sample should be obtained as core or endoscopic. Fine needle aspirations (FNA) samples are acceptable. The total number of core biopsies obtained should be approximately 6-15, with an average of 10.

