#### 12.5. **Criteria for Future Studies**

If the sample size is justified by precision only, state the outcomes that constitute success. If the protocol is part of a sequence of studies, state the statistical criteria that will be applied. If this is a pilot study, state what result would convince you to begin a fully powered study.

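### The null 6-month PFS of 20% is called observed, but Section 2.1 reports 26% from the same reference, and the gap is not explained

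*Combined protocol and SAP*

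**What the plan says.** Section 12.1 sets the null for the primary endpoint: "A 6-month PFS of 20% was observed using single agent pembrolizumab and is the basis for the null hypothesis of the present study". It names abstract 4001 as the source. The synopsis has the same sentence and cites reference 1, which the reference list identifies as abstract 4001. The synopsis and Section 12.1 both give the operating claim, "This design has 80% power to reject a 20% PFS rate, if the true PFS is 39" percent, using binomial probabilities at a one-sided 10% level with 30 patients.

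Section 2.1 describes the KEYNOTE-012 study of pembrolizumab alone, which "included a cohort of 39 patients with PD-L1 expressing advanced gastric cancer", and reports: "The 6-month PFS was 26%; median PFS was 1.9 months". That paragraph also closes with reference 1.

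Section 2.3.1 describes the same cohort under reference 57 but gives no 6-month PFS, so it does not settle the matter. Section 12.5, where a success criterion would belong, still holds template text: "If this is a pilot study, state what result would convince you to begin a fully powered study".

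**The concern.** One reference carries two values for the same quantity, and both are presented as observed results. The lower value became the null, and no reason is given.

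There is no randomized control, so the comparison with single-agent pembrolizumab rests entirely on this number. The 10% error level applies only if the single-agent rate in the enrolled population is close to 20%. If that rate is nearer 26%, rejecting 20% does not show that epacadostat adds anything. A result of 10 or 11 successes among 30 would reject a 20% null but not a 26% null, and the protocol's own text would support either reading.

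**Working it through.** **Inputs.** Sample size 30, one-sided level 10%, null p0 = 20% and alternative p1 = 39% (synopsis and Section 12.1); the competing single-agent rate of 26% in 39 patients (Section 2.1). Assumption: all 30 patients have a known 6-month status, so the number of successes X is binomial.

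**Formula.** The success rule is the smallest r with P(X ≥ r | n, p0) ≤ 0.10. Power is P(X ≥ r | n, p1). The protocol states no cutoff; those below are derived from its stated inputs.

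**Step 1: reproduce the plan's figure (p0 = 20%).**
- P(X ≥ 9 | 30, 0.20) = 0.1287, above 0.10.
- P(X ≥ 10 | 30, 0.20) = 0.0611, so r = 10.
- P(X ≥ 10 | 30, 0.39) = 0.7934, which matches the stated 80% after rounding.

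The calculation is sound. The doubt is about its input.

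**Step 2: keep the rule of at least 10 of 30 and vary the true single-agent rate.**

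| True rate | Chance of declaring success |
|---|---|
| 20% | 6.1% |
| 22% | 10.4% |
| 24% | 16.2% |
| 26% | 23.5% |

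The chance reaches 10% at a true rate of 21.8%.

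**Step 3: use 26% as the null with 30 patients.**
- P(X ≥ 11 | 30, 0.26) = 0.1317, above 0.10.
- P(X ≥ 12 | 30, 0.26) = 0.0660, so r = 12.
- P(X ≥ 12 | 30, 0.39) = 0.5242.
- P(X ≥ 12 | 30, p) = 0.80 at p = 0.460.

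**Step 4: sample size for 80% power, 26% against 39%.** The smallest n that meets both conditions is 61, with r = 21 (type I error 0.0903, power 0.8053). Exact binomial power moves in a saw-tooth: it is 75.6% at n = 62 and 79.9% at n = 69, and stays at or above 80% only from n = 70.

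**Step 5: precision of the 26%.** Taking 26% as 10/39 (assumption: a simple proportion without censoring), the Clopper-Pearson 95% interval is 13.0% to 42.1%.

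**Step 6: sensitivity to fewer evaluable patients.** Re-deriving the 20% rule at smaller n gives these chances of success at a true 26%: 20.0% at n = 29 (r = 10), 29.1% at n = 28 (r = 9), 25.2% at n = 27 (r = 9) and 21.4% at n = 26 (r = 9). The figure depends on n but is at least twice the nominal 10% throughout.

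**The case against.** The strongest reply is that 26% need not be the single-agent rate for this trial. It comes from patients whose tumours expressed PD-L1. This trial has no PD-L1 criterion in Sections 3.2 or 3.3, and Section 4.9.3 says: "Patients are not required to have PD-1 expression testing for enrollment on the study". A lower benchmark may therefore be sensible. The estimate is also imprecise, since its interval includes 20%. On this view 23.5% is one point in a sensitivity range and not the demonstrated error rate of the design.

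Much of that stands: 23.5% is conditional on a true rate of 26%, and 20% may prove defensible. But the protocol does not make the argument. It calls 20% observed, and an observed rate and a chosen benchmark are different claims. Imprecision does not explain two point values from one citation, and the same interval extends well above 26%, where the error would be larger.

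The populations also differ in more than PD-L1. Most of the earlier cohort had received at least two prior therapies, while this trial requires at least one line. Exclusions 3.3.3 and 3.3.5 do not bar all earlier pembrolizumab. A justification for 20% should address these differences too.

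It is also fair that the counts are inferred. Section 12.2.1 censors dropouts and uses Kaplan-Meier for median PFS, and Table 8 limits PFS to patients with a first follow-up scan. A fixed count works only if every patient in the analysis set has a known 6-month status. That is a separate question, and the counts given here depend on its answer.

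**Conclusion.** The inconsistency is real and must be resolved, because the figure in dispute is the sole comparator for the primary endpoint. The documents do not show whether 20% or 26% is what the source reports, and this review takes no position on that.

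With 30 patients, the choice between the two nulls moves the success threshold from 10 to 12 and power at 39% from 79.3% to 52.4%. If 20% is kept and the truth is 26%, the false-positive rate is 23.5% against a stated 10%. These figures assume exact binomial testing with all 30 patients counted. The case for correction rests on the undocumented comparator and does not require 26% to be the true rate.

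**What to change.** Check the cited abstract, then make the synopsis, Section 2.1 and Section 12.1 agree in one of three ways.

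1. **The source reports 20%.** Correct Section 2.1. State success as at least 10 of 30 (type I error 6.1%, power 79% at 39%).
2. **The source reports 26% and that is the relevant control rate.** Set the null at 26%. State success as at least 12 of 30 (type I error 6.6%) and restate power as 52% at 39%, reaching 80% at a true rate of 46%.
3. **The source reports 26% but 20% is kept as a benchmark.** Remove the claim that 20% was observed. Justify the discount, covering PD-L1 status, prior lines and prior pembrolizumab. State success as at least 10 of 30, and disclose that this rule's false-positive rate is 23.5% if the true single-agent rate is 26%.

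Put the chosen rule in Section 12.5 in place of the template text, and fix it before the outcome data are read. Recompute the counts if the primary analysis set is smaller than 30; if 6-month PFS is to be tested with a censored estimate, specify that test and restate its operating figures instead.

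**Cost.** Options 1 and 3 change wording only, though option 3 means publishing the 23.5%. Option 2 at 30 patients means accepting 52% power at the protocol's own target. Restoring 80% power for 26% against 39% would need at least 61 patients, or 70 to stay clear of the saw-tooth, which is about double the planned sample or somewhat more. None of the three options requires that.
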